6.5 POOLING OF CENTRES

This section is not applicable because centre/country is not included in the statistical model.

6.6 HANDLING OF MISSING DATA AND OUTLIERS

Generally, it is not planned to impute missing values for safety or efficacy evaluations with the exception of missing or incomplete AE dates and missing data of PK data. These will be handled according to BI standards (see SOP 001-MCG-156_RD-01 for missing AE dates ([3](#)) and SOP 001-MCS-36-472 for missing PK data ([4](#))).

6.7 BASELINE, TIME WINDOWS AND CALCULATED VISITS

For endpoints regarding pulmonary function testing (e.g. FEV₁) in-clinic, baseline is defined as the last measurement taken on day 1 before first study drug administration.

For all other endpoints, baseline is defined as the last measurement before first study drug administration. I.e., in case the pre-dose measurement on Day 1 is missing, the measurement between Day -17 and Day -11 will be used as baseline (note. Not possible for pulmonary function testing due to different bronchodilator washout requirements).

Time windows are defined in Section 6.1 of the CTP. Adherence to time windows will be checked at the MQRM.

7. PLANNED ANALYSIS

The format of the listings and tables will follow the BI guideline "Reporting of clinical trials and project summaries" ([7](#)).

The individual values of all subjects will be listed, sorted by treatment group, subject number and visit (if visit is applicable in the respective listing). AE listings will be sorted by assigned treatment (see [Section 7.8.1](#) below for details). The listings will be contained in Appendix 16.2 subject data listings (SDL) of the CTR.

Inferential statistical analyses of PK NCA endpoints will be presented in Section 15.5 of the CTR and in Appendix 16.1.9.3.

Descriptive data analysis of PK NCA endpoints will be presented in Section 15.6 of the CTR.

The following standard descriptive statistical parameters will be displayed in summary tables of continuous variables:

N	number of non-missing observations
Mean	arithmetic mean
SD	standard deviation
Min	minimum
Median	median
Max	maximum

For scores derived from questionnaire data, the following descriptive statistics will be calculated:

N	number of non-missing observations
Mean	arithmetic mean
SD	standard deviation

For plasma concentrations as well as for all PK parameters, the following descriptive statistics will additionally be calculated:

CV	arithmetic coefficient of variation
gMean	geometric mean
gCV	geometric coefficient of variation

The data format for descriptive statistics of plasma concentrations will be identical with the data format of the respective concentrations. The descriptive statistics of PK parameters will be calculated using the individual values with the number of decimal places as provided by the evaluation program. Then the individual values as well as the descriptive statistics will be reported with three significant digits in the CTR.

Tabulations of frequencies for categorical data will include all possible categories and will display the number of observations in a category as well as the percentage (%) relative to the respective treatment group. Percentages will be rounded to one decimal place. The category

missing will be displayed only if there are actually missing values. Percentages will be based on all subjects in the respective analysis set whether they have non-missing values or not.

7.4 PRIMARY ENDPOINT(S)

The primary endpoint to assess efficacy of BI 1265162 is the change from baseline in percent predicted trough Forced Expiratory Volume in 1 Second (FEV1) after 4 weeks of treatment. Trough FEV1 is defined as measurement performed within 30 minutes prior to dosing.

7.4.1 Primary analysis of the primary endpoint(s)

To account for the repeated nature of the data and the covariates in the nature, a restricted maximum likelihood (REML) based approach using a mixed model with repeated measurements (MMRM) will be carried out comparing the change from baseline in percent predicted trough FEV1 percent predicted at 4 weeks of treatment.

The analysis will include the fixed, categorical effects of treatment at each visit and the fixed continuous effects of baseline at each visit. Visit will be treated as the repeated measure with an unstructured covariance structure used to model the within-patient measurements. The model will only include data from highest dose level and placebo because of limited sample size from other dose levels.

The Kenward-Roger approximation will be used to estimate denominator degrees of freedom and adjust standard errors.

The MMRM analysis will be carried out in SAS and covariate-adjusted fixed effect estimates of average response for each dose group and the covariance matrix will be extracted from the fit.

The following SAS[®] code for MMRM will be used:

```
PROC MIXED DATA=alldata cl method=reml ocovtest;
  CLASS usubjid trtpso avisitn;
  MODEL ept = trtpso*avistin base*avistin /ddfm=kr solution;
  REPEATED avisitn /subject=usubjid type UN r rcorr;
  LSMEANS trtpso*avistin / pdiff=all om cl alpha=0.05;
RUN;
```

If the model failed to converge, the following covariance structures will be tested in order: UN → AR(1).

For subgroup analysis, same MMRM model will be carried out within each subgroup.

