6. GENERAL ANALYSIS DEFINITIONS

6.1 TREATMENT(S)

For basic study information on treatments to be administered please refer to Section 4 of the CTP.

Patient randomisation will start with only adult patients to either 200 µg bid of BI 1265162 or placebo in a 1:1 ratio. Enrolment of adolescent patients will be based on periodic reviews of adult patient safety data. The analysis plan for periodic safety reviews of adult patients will be described separately.

As soon as 28 patients are allocated to these two treatment arms, the remaining patients will be allocated to the other doses of BI 1265162 as well as the highest dose and placebo in a 1:1:1:1:1 ratio (14 patients per treatment arm). As a result, it was planned to have patients distributed in a 2:1:1:1:2 ratio (2 for either placebo or 200 µg bid of BI 1265162 and 1 for other doses of BI 1265162) with around 20% of adolescents per group.

Patients will be analysed according to [Table 6.3: 1](#). All planned analysis will be presented by this treatment group, unless specified otherwise. Handling of patients where treatment assignment has not been followed will be handled on a case-by-case basis, to be agreed at report planning meetings or DBL meeting (but prior to database lock).

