7.5.2 Secondary endpoint(s)

7.5.2.1 Analysis of LCI

An analysis of covariance (ANCOVA) will be used to compare the change from baseline of LCI after 4 weeks of treatment with adjustment for categorical effects of treatment and the fixed continuous effect of baseline. The model will include data from highest dose level and placebo. Descriptive analysis will be performed for other dose levels.

Tables and/or spaghetti plots will display individual LCI values over time. In addition, a waterfall plot for change from baseline at Week 4 will be presented.

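### The FEV1 MMRM and the LCI ANCOVA pool two randomisation stages without a stage term: no bias, but a slightly wider 200 µg versus placebo interval if the stages differ

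*SAP*

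**What the plan says.** SAP section 6.1 sets out the two stages. The first: "Patient randomisation will start with only adult patients to either 200 µg bid of BI 1265162 or placebo in a 1:1 ratio". The second: "As soon as 28 patients are allocated to these two treatment arms, the remaining patients will be allocated to the other doses" of the drug, "as well as the highest dose and placebo in a 1:1:1:1:1 ratio (14 patients per treatment arm". For the overall result, "it was planned to have patients distributed in a 2:1:1:1:2 ratio".

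Section 7.4.1 restricts the primary MMRM to the highest dose and placebo and describes its fixed effects: "The analysis will include the fixed, categorical effects of treatment at each visit and the fixed continuous effects of baseline at each visit". The SAS code agrees: "MODEL ept = trtpso*avistin base*avistin /ddfm=kr solution". No stage variable appears in the MODEL or CLASS statement.

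Section 7.5.2.1 specifies the LCI ANCOVA for the same two arms "with adjustment for categorical effects of treatment and the fixed continuous effect of baseline".

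Section 4 removes the age effect from the model, and section 7.5.2.4 notes that no adolescent was randomised. The SAP does not say why stage is left out and gives no estimate of a difference between stages.

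**The concern.** The stage in which a patient was randomised is part of the allocation scheme and is known for everyone. The two compared arms are planned in equal numbers within each stage, so the design cancels any stage difference from the treatment contrast. A model without stage does not use this: it counts the difference between stages as unexplained variation among patients. The standard error is then larger than the design requires whenever the stages differ in change from baseline.

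At stake is the precision of the only efficacy comparison that the SAP still models, 200 µg versus placebo, with 28 patients per arm as planned.

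**Working it through.** **Inputs.** Stage 1: 28 patients, 1:1 (section 6.1). Stage 2: 14 per arm, 1:1:1:1:1 (section 6.1). Model terms: sections 7.4.1 and 7.5.2.1. Confidence level 95% (alpha=0.05 in the section 7.4.1 code). The SAP gives no SD or stage shift, so widths are in residual SDs and the shift *d* is assumed over a range.

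**The plan's own figure.** Stage 1 gives 28/2 = 14 in each of two arms. Adding 14 per arm in stage 2 gives 28:14:14:14:28 = 2:1:1:1:2, as stated. The total is 98 patients, 56 of them in the MMRM.

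**Bias.** A stage shift *d* moves the contrast without a stage term by *d* × (stage 2 share in 200 µg − stage 2 share in placebo) = *d* × (14/28 − 14/28) = 0.

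**Precision.** I use the Week 4 ANCOVA as a single-visit approximation to the MMRM. Let *n* be the number per arm, *N* = 2*n*, and *p* the stage 2 share.

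- With stage: half-width = t(0.975, *N*−4) × √(2/*n*).
- Without stage: half-width = t(0.975, *N*−3) × √(2/*n*) × √[1 + *N p*(1−*p*)*d*²/(*N*−3)].

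For *n* = 28, *N* = 56, *p* = 0.5 and *d* = 0.5:

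- The factor under the root is 1 + 56 × 0.25 × 0.25/53 = 1.066, with square root 1.0325.
- Without stage, the half-width is 0.5361 × 1.0325 = 0.5535 SD.
- With stage, it is 0.5363 SD.
- The ratio is 1.032.

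Ratio of half-widths, without stage to with stage:

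| Stage 2 per arm | d = 0 | 0.25 | 0.5 | 0.75 | 1.0 |
|---|---|---|---|---|---|
| 14 (planned) | 0.9996 | 1.0078 | 1.0320 | 1.0712 | 1.1238 |
| 7 (assumed) | 0.9992 | 1.0066 | 1.0286 | 1.0643 | 1.1123 |
| 4 (assumed) | 0.9988 | 1.0047 | 1.0221 | 1.0504 | 1.0889 |

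The stage term starts to pay at a shift of about 0.06 SD with 14 per arm in stage 2, and about 0.11 SD with 4 per arm.

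**Simulation check** (8,000 trials per setting, baseline covariate in the model). With 14 per arm in stage 2, the ratios were 0.9997, 1.0077, 1.0312 and 1.1215 at *d* = 0, 0.25, 0.5 and 1.0. Mean error of the estimate was close to zero with and without the term. Coverage without stage was 94.7%, 95.2%, 95.5% and 96.9%. With stage it was 94.7%, 95.1%, 94.9% and 95.0%. The Monte Carlo error on coverage is about 0.24 percentage points (√(0.95 × 0.05/8000)).

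**In patients.** At *d* = 0.5, 1.032² = 1.065, so the lost precision is worth about 6.5% of the sample: 0.065 × 56 ≈ 3.6 patients.

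**The case against.** The strongest reply is that the SAP contains no error here. The model is standard and baseline-adjusted, its text and code agree, its estimate is unbiased and its coverage is nominal or conservative. A covariate that only improves precision is optional. That stands, and it limits the point to a minor improvement.

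It also stands that nothing in the SAP shows a shift. The most obvious source, adolescents entering after an adult-only start, is ruled out because none was randomised. Baseline is already in the model, so a shift would have to lie in the four-week change itself. Other differences between successive cohorts are neither shown nor excluded.

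A reader might infer more in three ways, none supported by the documents:

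- *That the interval is in fact too wide.* This is so only if a shift exists. With no shift, the stage term makes the interval very slightly wider.
- *That changing the allocation ratio confounds treatment with calendar time.* The ratio changes for the lower doses, but 200 µg to placebo stays 1:1 in both stages, and only these two arms enter the models.
- *That stage 2 closed short and left the arms unbalanced by stage.* Section 7.4.1 cites the limited sample size at the other doses, but the planned 14 per arm against 28 would also explain that remark. Actual stage sizes are not given.

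The remaining objection is that stage-by-visit terms would rest on few patients if stage 2 was small. This has little force: with 4 per arm in stage 2, the cost at zero shift is about 0.12% of the interval width.

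The protocol is not at hand, so whether stage was a formal stratum or simply a change of allocation list cannot be seen. The arithmetic needs only equal allocation of the two arms within each stage.

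**Conclusion.** The point holds as a conditional matter of precision. Both models pool two randomisation stages without a stage term. The treatment estimate is unbiased and type I error is not inflated. If the stages differ in mean change from baseline after baseline adjustment, the 200 µg versus placebo interval is wider than necessary and slightly conservative. The loss is about 3% or less for shifts up to 0.5 SD and reaches about 7% at 0.75 SD with the planned numbers; a smaller stage 2 reduces it.

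This rests on an assumed shift, on equal allocation within each stage as planned, and on the single-visit approximation. The priority is low, and the case for acting is that the change costs almost nothing.

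**What to change.** Define randomisation stage as first 28 patients versus later. In section 7.4.1, add stage by visit as a fixed categorical effect in the MMRM and list stage in the CLASS statement. In section 7.5.2.1, add stage to the LCI ANCOVA. Include no treatment-by-stage term, so that the result remains one overall 200 µg minus placebo difference at Week 4.

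If the primary model can no longer be changed, specify the same models as a sensitivity analysis before treatment-level results are seen.

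The cost is one SAP sentence, one term in each model and one degree of freedom per visit: about 0.04% to 0.12% on the interval width if the stages do not differ. Stage follows from the randomisation order, so no new data are needed, and the quantity estimated does not change.

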5. ENDPOINTS(S)

5.1 PRIMARY ENDPOINT(S)

The primary endpoint to assess efficacy of BI 1265162 200 µg bid over placebo is the absolute change from baseline in percent predicted trough Forced Expiratory Volume in 1 Second (FEV₁) after 4 weeks of treatment.

Trough FEV₁ is defined as measurement performed within 30 minutes prior to dosing.

Analysis is conducted using a restricted maximum likelihood (REML) based approach using a mixed model with repeated measurements (MMRM). Please refer to [Section 7.4.1](#) for details on the MMRM model.

Tables and/or spaghetti plots will display individual trough FEV₁ % predicted values over time and the change from baseline values overtime. In addition, a waterfall plot for change from baseline at Week 4 will be presented.

Baseline trough FEV₁ % predicted is defined as the last measurement taken on day 1 before first study drug administration.

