7.8.1 Adverse Events

AEs will be coded with the most recent version of MedDRA.

The analyses of AEs will be descriptive in nature. All analyses of AEs will be based on the number of subjects with AEs and not on the number of AEs.

The analysis of AEs will be based on the concept of treatment emergent AEs. That means that all AEs occurring between first drug intake till 7 days after last drug intake will be assigned to the randomised treatment. All AEs occurring before first drug intake will be assigned to 'screening' and all AEs occurring after last drug intake + 7 days will be assigned to 'follow-up' (for listings only).

An overall summary of AEs will be presented. This overall summary will comprise summary statistics for the class of other significant AEs according to ICH E3 and for the class of adverse events of special interest (AESI). For the definition of AESI please refer to Section 5.2.6.1.4 of the CTP.

The frequency of subjects with AEs will be summarised by treatment (dose), primary system organ class and preferred term. AEs which were considered by the investigator to be drug related will be summarised separately. Separate tables will also be provided for subjects with serious AEs (SAEs), subjects with AESIs and subjects with other significant AEs (according to ICH E3). AEs will also be summarized by maximum intensity.

The system organ classes will be sorted according to the standard sort order specified by the European Medicines Agency (EMA), preferred terms will be sorted by total frequency (within system organ class).

A further table will present AEs by preferred term, dose group and intensity, sorted by descending relative frequency in any dose group.

Adverse events ongoing at Visits 2 (baseline), 3 (week 1) and 4 (week 4) will be provided to help explaining outliers regarding efficacy.

For disclosure of AE data on ClinicalTrials.gov, the frequency of subjects with non-serious AEs occurring with an incidence of greater than 5 % (in preferred terms) will be summarised by treatment, primary system organ class and preferred term. The frequency of subjects with SAEs will also be summarised.

For disclosure of AE data in the European union drug regulating authorities clinical trials (EudraCT) register, the frequency of AEs, the frequency of non-serious AEs with an incidence of greater than 5 % (in preferred terms) and the frequency of SAEs will be summarised.

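### Does the printed SAS code in SAP Section 7.4.1 leave the two-arm primary model, or its Week 4 contrast, undetermined?

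*SAP*

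**What the plan says.** Section 7.4.1 fixes the arms in one sentence, "The model will only include data from highest dose level and placebo because of limited sample size from other dose levels", and gives the purpose of the MMRM as "comparing the change from baseline in percent predicted trough FEV1 percent predicted at 4 weeks of treatment". Section 5.1 names the pair of arms: efficacy of 200 µg "bid over placebo is the absolute change from baseline in percent predicted trough Forced Expiratory Volume in 1 Second", after 4 weeks. Section 7.5.2.1 uses the same two arms for LCI and describes the other doses only with summary statistics.

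Later in Section 7.4.1 the output is described as "covariate-adjusted fixed effect estimates of average response for each dose group and the covariance matrix will be extracted from the fit", and the section states that the SAS "code for MMRM will be used". That code opens with "PROC MIXED DATA=alldata cl method=reml ocovtest", contains no subset by arm, and ends with "LSMEANS trtpso*avistin / pdiff=all om cl alpha=0.05".

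**The concern.** Section 6.1 describes a five-arm trial, so a data set named `alldata` can be read as holding five arms. The output sentence speaks of each dose group and a covariance matrix, and mentions neither a treatment difference nor its interval. The `pdiff=all` option prints every pair of treatment-by-visit means, and nothing marks which row is the primary result.

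A second programmer who took the code literally might fit all five arms. The baseline slope and the within-patient covariance would then be pooled over more patients. The estimate for the highest dose against placebo, its standard error and its degrees of freedom would differ from those of the two-arm fit in the text. At stake is whether two people working from the SAP would report the same primary figures.

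**Working it through.** **1. Is the primary contrast identified?** The text fixes each element.

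- Arms: highest dose and placebo (Section 7.4.1); 200 µg bid over placebo (Section 5.1).
- Time: 4 weeks (both sections).
- Variable: change from baseline in trough FEV₁ % predicted (both sections).

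Two arms at one time point give C(2,2) = 1 treatment difference.

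**2. What does the code print?** Cells = arms × post-baseline visits; differences = C(cells, 2). I assume two modelled visits, Week 1 and Week 4, because Section 7.8.1 lists "Adverse events ongoing at Visits 2 (baseline), 3 (week 1) and 4 (week 4"). Three visits are shown as the range.

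| Arms | Visits | Cells | Differences | Same-visit | Cross-visit |
|---|---|---|---|---|---|
| 2 | 2 | 4 | 6 | 2 | 4 |
| 5 | 2 | 10 | 45 | 20 | 25 |
| 2 | 3 | 6 | 15 | 3 | 12 |
| 5 | 3 | 15 | 105 | 30 | 75 |

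In every case exactly one row is the highest dose against placebo at Week 4. It is labelled by treatment and visit, and `cl alpha=0.05` adds its 95% limits.

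**3. What if five arms were fitted by mistake?** The planned numbers in Section 6.1 are 14 + 14 = 28 in each main arm and 14 in each of three lower-dose arms, 98 in total. The SAP does not give the numbers achieved, so I let the lower arms range from 2 to 14.

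With complete data the MMRM gives the Week 4 ANCOVA result. The two fits then differ only in the baseline slope. The pooled slope is the efficient one, so the variance of the difference between slopes is the difference of their variances. With ν = N − arms and a normally distributed baseline, in residual-SD units:

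SD of the difference between estimates = √{[1/(ν₂ − 2) − 1/(ν₅ − 2)] × 2/n}

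Here n = 28 and ν₂ − 2 = 56 − 2 − 2 = 52. For 14 per lower arm, ν₅ − 2 = 98 − 5 − 2 = 91, so √[(1/52 − 1/91) × 2/28] = 0.0243. The simulated columns come from 20,000 trials per setting with a true difference of 0.75 SD, slope −0.3 and about 78% power. Residual df = N − arms − 1, against 56 − 2 − 1 = 53 for the two-arm fit.

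| Per lower arm | N | ν₅ − 2 | Formula SD | Simulated SD | Residual df | Opposite sides of two-sided 0.05 |
|---|---|---|---|---|---|---|
| 2 | 62 | 55 | 0.0087 | 0.0087 | 56 | 1.1% |
| 5 | 71 | 64 | 0.0160 | 0.0160 | 65 | 2.4% |
| 8 | 80 | 73 | 0.0199 | 0.0198 | 74 | 2.9% |
| 14 | 98 | 91 | 0.0243 | 0.0240 | 92 | 3.7% |

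The standard error is about √(2/28) = 0.267, so the shift is 0.0087/0.267 = 3% to 0.0240/0.267 = 9% of it. The five-arm interval is 0.2% to 1.2% narrower, or 0.1% to 0.8% if the width ratio is averaged within each trial.

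With an assumed 20 per main arm, ν₂ − 2 = 36 and the formula gives √[(1/36 − 1/39) × 2/20] = 0.015 to √[(1/36 − 1/75) × 2/20] = 0.038.

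**4. Would anyone run the listing literally?** As it appears, it would not run. The model and LSMEANS lines use `avistin` where the CLASS line has `avisitn`, and `type UN` lacks an equals sign. Some of this may come from reading the PDF. The listing also shows no Treated Set restriction, which Section 6.3 supplies in words. It works as a template whose input is defined by the surrounding text.

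**The case for a change.** The best case for a change is that Section 3 promises detailed procedures for executing the analysis, so a primary result should be reproducible without inference. Section 4 drops the dose-response test described in the protocol, which is a reason to say plainly what the primary output now is. The output sentence instead lists group estimates and a covariance matrix. One code line and two wording edits would cost almost nothing.

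Part of this stands. The listing does not display the two-arm restriction and does not mark the Week 4 row, and a WHERE condition would be harmless and slightly clearer.

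The rest does not stand:

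- The contrast is named once Sections 5.1 and 7.4.1 are read together.
- The reference to each dose group can mean each group in the fit; Section 7.8.2 uses the term in the same loose way for the groups compared.
- `alldata` is only a name, and the data may be subset before the call.
- Extra printed differences do no harm, because the plan makes no use of the cross-visit ones, and one labelled row is easily selected by program.
- The disagreement rates at 0.05 depend on an effect size and a decision rule that the SAP does not state. The highest rate also needs the lower arms at their full planned size, although Section 7.4.1 excludes them for limited sample size.

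**Conclusion.** No change to the plan follows. The text fixes the model, the arms and the time point, and anyone who follows it reaches one sound primary estimate with its 95% confidence interval. What remains is a clerical gap between prose and listing that a programmer closes by reading the sentence on arms in the same section.

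Even the misreading would have little effect. It would typically move the estimate by 0.009 to 0.024 residual SD at 28 per main arm, or up to 0.038 at an assumed 20, and would leave a valid estimate of the same difference. These sizes rest on complete data, a common baseline slope and assumed lower-arm numbers of 2 to 14. The count of printed differences rests on two or three modelled visits. The conclusion that the contrast is identified needs none of these assumptions.

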7.5.2.4 Analysis of Questionnaires (CASA-Q[©] and CFQ-R)

CASA-Q

The derivation of the CASA-Q domain scores will be performed according to the CASA-Q[©] user manual ([11](#)). All reported answers will be listed together with the derived domain scores.

Descriptive analysis will be done by treatment and domain score for baseline, Day 8, Day 29 and change from baseline.

CFQ-R

As no adolescent randomized, CFQ-R Teen/Adult version will be used.

The derivation of the CFQ-R scores will be performed according to the CFQ-R scoring instructions ([12](#)). The CFQ-R total score is the sum of each domain score. All reported answers will be listed together with the derived scores.

Descriptive analysis will be done by treatment and score for baseline, Day 29 and change from baseline and will be presented separately for total score and each domain score.

To explore the relationship between primary endpoint and CFQ-R respiratory domain score, a scatter plot of baseline CFQ-R respiratory domain score against change from baseline in FEV1 % predicted after 4 weeks of treatment.

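### Should AR(1) be replaced as the only fallback if the primary MMRM fails to converge?

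*SAP*

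**What the plan says.** Section 7.4.1 analyses trough FEV1 % predicted by REML, with treatment-by-visit and baseline-by-visit effects, Kenward-Roger degrees of freedom, and data from the highest dose and placebo only. On the covariance it says: "Visit will be treated as the repeated measure with an unstructured covariance structure used to model the within-patient measurements". The contrast of interest is at Week 4. On non-convergence it says: "If the model failed to converge, the following covariance structures will be tested in order: UN → AR(1". No robust standard error and no single-visit model is named as a further step. The section also states: "For subgroup analysis, same MMRM model will be carried out within each subgroup".

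Section 7.4.1 does not list the visits in the model. Two other places suggest two post-baseline visits. Section 7.5.2.4 summarises CASA-Q as follows: "Descriptive analysis will be done by treatment and domain score for baseline, Day 8, Day 29 and change from baseline". Section 7.8.1 states: "Adverse events ongoing at Visits 2 (baseline), 3 (week 1) and 4 (week 4) will be provided to help explaining outliers regarding efficacy".

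For LCI, Section 7.5.2.1 uses a simpler model on the same two arms: "An analysis of covariance (ANCOVA) will be used to compare the change from baseline of LCI after 4 weeks of treatment", adjusted for treatment and baseline.

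**The concern.** The unstructured model is the one that has just failed, so the list offers a single alternative. With two visits AR(1) is the same as compound symmetry: one variance and one correlation. Its decay over time never comes into play, and the only thing it changes is to make the Week 1 and Week 4 variances equal. Kenward-Roger corrects for small samples, not for a wrong covariance. If Week 4 is more variable than Week 1, the Week 4 confidence interval would be too narrow; if less variable, too wide. The SAP already holds a Week 4 model, for LCI, that avoids the assumption, so the choice looks easy to improve.

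**Working it through.** **Inputs.** Section 6.1 of the SAP plans 28 patients randomised 1:1 (14 per arm), then 14 more per arm, so 14 + 14 = 28 per arm for the highest dose and placebo. The following are assumptions, because the SAP does not give them: two post-baseline visits, correlation 0.6 between visits, the SD ratio R = SD Week 4 / SD Week 1, and 10% missing values. The SAP states no figure on this point to reproduce.

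**Step 1: size of the bias if AR(1) is reported.** With complete data and visit-specific treatment and baseline effects, the Week 4 estimate is the same under both structures. AR(1) replaces the Week 4 variance by the average of the two visit variances, so

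SE ratio = sqrt((1 + R²)/2) / R, and asymptotic type I error = 2 × (1 − Φ(1.96 × SE ratio)).

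| R | SE ratio | Type I error |
|---|---|---|
| 0.8 | 1.132 | 2.7% |
| 0.9 | 1.057 | 3.8% |
| 1.0 | 1.000 | 5.0% |
| 1.1 | 0.956 | 6.1% |
| 1.25 | 0.906 | 7.6% |

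Simulated REML fits at 28 per arm with 10% missing at Week 4 agree within simulation error of about 3%. At R = 1.25 the mean SE over the empirical SD was 0.914 under AR(1) and 1.011 under the unstructured model. At R = 0.8 these were 1.104 and 0.968.

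The table describes AR(1) applied to complete data. There the unstructured REML fit has a closed form and does not fail, so those datasets would not reach the fallback. The table shows direction and rough size only.

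**Step 2: how often the fallback is reached.** Two visits need three covariance parameters. Unstructured fits that failed (general optimisers, not PROC MIXED):

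- 28 per arm: 0/400, 0/2,000 and 0/200, together 0/2,600. Upper 95% bound about 3/2,600 = 0.12%.
- 14 per arm: 0/400 and 0/500, together 0/900. Upper bound about 3/900 = 0.33%.
- 7 per arm: 1/400 and 0/1,200.
- 4 per arm: 33/400 (8%) in one run. In a second, 158/4,000, 96/2,500 and 103/2,500, together 357/9,000 (4%). The rate depends on the failure criterion.

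**Step 3: behaviour in the fits that reach it.** Among the failed fits at 4 per arm in the second run, AR(1) itself failed in 13% to 16%. Rejections under the null:

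| R | AR(1) | Week 4 ANCOVA |
|---|---|---|
| 1.25 | 15/132 (11.4%) | 9/158 (5.7%) |
| 1.0 | 4/83 (4.8%) | 4/96 (4.2%) |
| 0.8 | 6/90 (6.7%) | 3/101 (3.0%) |

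**Step 4: combined effect.** Take the worst row, an excess of 11.4 − 5.0 = 6.4 points. In the main analysis it contributes at most 0.0012 × 6.4 = 0.008 percentage points to type I error. At 4 per arm it contributes 0.04 × 6.4 = 0.26 to 0.0825 × 6.4 = 0.53 points.

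**Step 5: price of the substitute.** In the fits from Step 3, the median Week 4 ANCOVA half-width at R = 1.0 was 2.61 against 1.93 for AR(1): 2.61/1.93 = 1.35, or 35% wider. It was 17% wider at R = 0.8 and 52% wider at R = 1.25, the last partly because AR(1) is too narrow there.

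**The case for a change.** The best case for a change is that a fallback exists only for the day it is needed, so it should be sound then. Section 7.4.1 runs the same model within subgroups, where fits can be small. ANCOVA held its level, is already programmed for LCI, and would cost one sentence. Its precision loss against a converged unstructured model is small: sqrt([1/(1 − m)] / [(1 − 0.36)/(1 − m) + 0.36]) − 1 gives 1.8% for m = 10% missing at Week 4 and 3.8% for m = 20%.

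Part of this stands. AR(1) is too liberal if Week 4 is clearly more variable, and the small-fit simulation supports that direction. The rest is weaker. The 1.8% to 3.8% compares with a model that, by definition, is not available when the fallback applies; the relevant comparison is with AR(1), in Step 5. ANCOVA drops patients without a Week 4 value and needs missingness to be unrelated to Week 1 response given treatment and baseline. It would do so in just the sparse, incomplete data that trigger the fallback. The available SAP text gives no subgroup sizes and attaches no formal test to subgroup fits, so 4 per arm is a supposition. The other candidates do not help much either. With two visits, heterogeneous AR(1) or compound symmetry only rewrites the unstructured model. An uncorrected sandwich error gave about 8% type I error at 7 per arm and 11% at 4.

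**Conclusion.** The observation about AR(1) is correct, but no change to the SAP follows. At the planned 28 per arm, and even at half that, the fallback was never reached in simulation, and its possible effect on the primary type I error is below 0.01 percentage point. It could matter only in subgroup fits of about 4 per arm, by roughly 0.3 to 0.5 points in the least favourable variance setting tried. There the choice lies between a model that pools variance across visits and uses all observed data, and one that is free of the equal-variance assumption but wider and more demanding about missing data. Either is defensible, and an analyst who did reach the fallback could report a Week 4 ANCOVA beside it.

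This rests on two post-baseline FEV1 visits (inferred, not stated in Section 7.4.1), correlation 0.6, about 10% missing values, SD ratios between 0.8 and 1.25 in the rejection counts, and convergence behaviour in PROC MIXED similar to that of the optimisers used.
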